#### 9.2 Concurrent Illnesses and Medical Conditions

All current illnesses and past pre-existing medical conditions will be coded using MedDRA® dictionary version 19.1 or higher. Summaries of participant's pre-existing medical conditions will be presented by MedDRA® system organ class (SOC) and preferred term (PT) and treatment group (Table 14.1.5) for all participants in the FA population.

Individual data listings will be presented for all pre-existing medical conditions (Listing 16.2.4.2).

#### 9.3 Measurements of Treatment Compliance

All participants were to receive a single dose of study product administered in the clinic. Any participants who were enrolled but not vaccinated will be presented by treatment group and by site as part of the

participant disposition table (Table 14.1.3).A summary of the dates of vaccination will be presented by treatment group in Table 14.1.6.

#### 9.4 Adverse Events

All safety analyses will be presented using the FA population.

Any medical condition that is present at the time that the participant is screened will be considered baseline and not reported as an AE, unless it worsens in severity or increases in frequency during the study. A treatment-emergent adverse event is one that is observed after baseline or worsens in severity or increases in frequency during the study. Solicited and unsolicited adverse events (AEs) will be analyzed separately. When calculating the incidence of AEs (i.e., on a per participant basis), each participant will be counted once and any repetitions within a participant will be ignored; the denominator will be the total population size. For tables summarizing severity, the severity will be summarized as the maximum severity experienced by that participant for a particular AE or symptom. All adverse events reported will be included in the summaries and analyses.

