#### STUDY PROCEDURES & VISIT SCHEDULE

After volunteers have signed the written informed consent, they will be screened for eligibility into the study. Screening will take place within 28 days prior to vaccination (Visit 1; Screening). A blood sample (up to 18 mL) will be taken at the screening visit for laboratory testing.

The following assessments will be conducted during the screening visit: medical history, physical examination, vital signs measurement and laboratory evaluation including hematology, serum chemistry and viral serology for Human immunodeficiency virus (HIV), Hepatitis B virus (HBV), and Hepatitis C virus (HCV). A test for pregnancy will be performed among females of child bearing potential. Inclusion/exclusion criteria will be assessed for eligibility.

At Visit 2 (Vaccination), eligible volunteers will be randomized in a 1:1:1 ratio to either one of the following groups:

Group	Vaccine
1 (n=20)	Adjuvanted Study vaccine (MCV-5)
2 (n=20)	Non-adjuvanted Study vaccine (MCV-5)
3 (n=20)	Reference vaccine (Menactra®, ACYW)

Baseline blood sample (20 mL) for immunogenicity testing will be collected before randomization on the day of vaccination and thereafter vaccine will be given as a single intramuscular injection of 0.5 mL in the deltoid. The day of vaccination will be considered as Day 1. After vaccination, participants will be observed for 60 minutes at the clinic to detect any immediate reactions or any other AE. All relevant information will be reported in the Case Report Form (CRF). A Memory Aid will be distributed and participants will be instructed to record post-immunization reactions, adverse events and concomitant medications. Participants will be informed to return to study centre for Visit 3 (Day 8).

At Visit 3 (Day 8), participants will undergo a targeted physical examination, vital sign measurement and a blood sample will be collected (up to 8 mL) to repeat the safety laboratory evaluations. Memory Aid records will be discussed with the participants, if needed, reconciled by the investigator/designee before recording in source document and transcribed into the CRF.

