## 5.2.2. Screening, Visit 1 (Day -28 to -1)

Once informed consent has been obtained the participant will be considered enrolled in the trial. The following procedures will be completed during screening to determine study eligibility and may occur over multiple screening visits. Additional screening visits may be scheduled for any follow up as needed, but are not required. At the screening visit(s), the PI or designee will provide prospective volunteers with a detailed description of the study objectives and study participation requirements, as well as potential health risks and benefits associated with study participation. Baseline data are obtained during screening, which may occur over the course of several contacts/visits, between 28 days prior to and on Day 1, the day of vaccination. All inclusion/exclusion criteria must be assessed from data obtained within that period, unless otherwise specified in the eligibility criteria. After study information has been provided and the appropriate informed consent has been obtained, the following procedures are performed by PI/designee:

- a) Confirms that written informed consent has been given and solicits and discusses any remaining questions the participant may have;
- b) Assign screening number once study specific consent form has been signed;
- c) Obtain demographic and contact (e.g., address, telephone, email) information;
- d) Obtain medical history; including history of any vaccination in the last 30 days and ever received vaccination against *Neisseria meningitidis*, tetanus or diphtheria containing vaccines
- e) Obtain history of medication use in the past 30 days;
- f) Measure height & weight;
- g) Perform full physical exam, including vital signs (blood pressure, pulse and temperature section 5.5.1); and
- h) Collect blood samples (18 mL) for screening laboratory testing: hematology (hemoglobin, platelet count and WBC), clinical chemistry (creatinine, albumin, ALT and total bilirubin), serum HCG pregnancy test (females of childbearing potential only) and screening for HIV, HCV and HBV (Appendix I).

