#### 5.2.4. Vaccination, Visit 2 (Day 1)

#### **Prior to Vaccine Administration**

- a) Obtain interim medical and medications history to confirm continued eligibility;
- b) Measure vital signs;
- c) Perform targeted physical exam based on complaints, interval history and to confirm absence of abnormality at the injection site (deltoid);
- d) For female participants of child bearing potential, perform urine or serum pregnancy test;
- e) Obtain blood samples (20 mL) for immunological testing; and
- f) Record randomization code for eligible participant

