#### 8.3. Definitions

#### 8.3.1. Adverse Event (AE)

An adverse event is any untoward medical occurrence in humans, whether or not considered vaccine related, that occurs after the vaccination during the conduct of a clinical trial. Any change from baseline assessment of clinical status, ECGs, routine laboratory tests, X-rays, physical examinations, etc., that is considered clinically significant by the PI is considered an AE.

**Suspected adverse drug reaction** is any AE for which there is a reasonable possibility that the vaccine caused the AE. A reasonable possibility implies that there is evidence to suggest that the study product caused the event.

Adverse reaction is any AE caused by the vaccine.

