#### 3.3 Study Definitions and Derived Variables

The following definitions and derivations will be used in this study:

- The baseline value will be defined as the last value obtained prior to the vaccination of study product.
- The reference day will be the day of vaccination and will be referred to as Day 1.
- Study days prior to vaccination will be calculated by taking the date minus the vaccination date (reference day).
- Study days occurring on or after the date of vaccination will be calculated by taking the date minus the vaccination date (reference day) and adding 1.
- Age will be calculated from the date of enrollment and will be presented in whole years (truncated integer).
- The calculations for GMTs will be performed by taking the anti-log of the arithmetic mean of the natural log-transformed titers.
- Fold increase will be calculated as the ratio of:  $\frac{post-immunizationrSBAtiter}{pre-immunizationrSBAtiter}$
- Seroconversion (4-fold response) will be defined as the following:
  - $\circ$  For participants with a pre-vaccination rSBA titer < 8, a post-vaccination titer  $\geq 32$ ;
  - For participants with a pre-vaccination rSBA titer ≥ 8, an increase in rSBA titer of at least
     4 times the pre-vaccination titer.
- Seroprotection will be defined as a rSBA titer of  $\geq 8$  and  $\geq 128$ .
- Prior medications are those medications that started and stopped prior to vaccination.

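### SAP 9.4 sets the adverse-event baseline at screening rather than at vaccination, so a condition that clears before the dose and returns after it can go unreported

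*SAP*

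**What the plan says.** SAP 9.4 gives the rule for pre-existing conditions: "Any medical condition that is present at the time that the participant is screened will be considered baseline and not reported as an AE". The only exceptions are worsening severity or increased frequency during the study. The next sentence reads: "A treatment-emergent adverse event is one that is observed after baseline or worsens in severity or increases in frequency during the study". Neither sentence names vaccination. The paragraph ends: "All adverse events reported will be included in the summaries and analyses".

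On timing, the protocol synopsis states: "Screening will take place within 28 days prior to vaccination". Protocol 5.2.2 carries Day -28 to -1 in its title, but its text is wider: "Baseline data are obtained during screening, which may occur over the course of several contacts/visits, between 28 days prior to and on Day 1".

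Other parts of the plan use vaccination as the anchor:

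- SAP 3.3: "The baseline value will be defined as the last value obtained prior to the vaccination of study product".
- Protocol 8.3.1, repeated in SAP 4.5.1.2, limits an AE to an occurrence "that occurs after the vaccination during the conduct of a clinical trial".
- Protocol 8.2 starts safety reporting at vaccination.
- Protocol 5.2.4 updates the participant's status on Day 1 before the dose: "Obtain interim medical and medications history to confirm continued eligibility". Vital signs and a targeted examination are also done then.

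**The concern.** Unsolicited AEs over 28 days are part of the primary endpoint (Protocol 2.4.4, SAP 3.2.1). A baseline rule for such events should separate what was there at the moment of exposure from what came afterwards. SAP 9.4 instead looks back to a visit that may be four weeks earlier, and it does not ask whether the condition was still present at the dose.

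Take blood pressure that is raised at screening, normal on Day 1 and raised again on Day 8, and that the investigator considers clinically significant. It arose after vaccination, so it meets the AE definition in both documents. Under SAP 9.4 it is a baseline condition and is not reported, unless a second episode is taken to be an increase in frequency. The SAP gives no reference period for judging frequency. Protocol section 8 has no screening-based exclusion, so the SAP is narrower than the protocol on this point.

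What is at stake is a modest understatement of absolute AE rates. In a descriptive first-in-human study those rates are the main product.

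**Working it through.** **1. The plan's own figures.** SAP 5 and Protocol 7.4 give n = 20 per group, a chance above 90% of seeing an AE with an 11% rate, and an upper bound of about 14% when none is seen.

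- 1 − 0.89^20 = 0.903. This reproduces.
- 1 − 0.05^(1/20) = 0.139 (one-sided 95%). This reproduces.

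Neither figure depends on the AE baseline, and neither changes if the baseline moves.

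**2. Gap between the two anchors.** The maximum is 28 days (the screening window). It can be close to zero, because Protocol 5.2.2 lets screening contacts run up to Day 1. The time of screening is therefore not one fixed point for every participant.

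**3. The rules side by side.**

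| Course of the condition | SAP 9.4, read literally | AE definition and reporting period |
|---|---|---|
| Present at screening and at the dose, unchanged after | Baseline, not an AE | Not an AE |
| Absent at screening and at the dose, starts after | Treatment-emergent | AE |
| Present at screening, absent at the dose, back after at the same severity | Baseline, not reported, unless called more frequent | AE |
| Absent at screening, starts before the dose, unchanged after | Meets the treatment-emergent wording | Not an AE |

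The third row is where an event can be lost. The fourth is a clash of wording, taken up in the verdict.

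**4. Which events are exposed.** Solicited reactions are largely protected, because they are collected on their own forms for seven days whatever the history (Protocol 8.1). For laboratory tests the two anchors normally coincide: the only scheduled pre-dose sample is the screening sample (Protocol Appendix I), so it is also the last value before vaccination. The exposed group is unsolicited clinical conditions and vital-sign findings.

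**5. Size.** The documents give no rate for the third row. As an assumption, let k participants in an arm of 20 have such a recurrence under one preferred term, with no other event of that term in the arm. The arm would be reported as 0/20 when k/20 is right. The two-sided exact 95% limits are the Beta quantiles B(0.025; k, 21 − k) and B(0.975; k + 1, 20 − k). The one-sided 95% upper bound is B(0.95; k + 1, 20 − k).

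| k | Proportion | Two-sided exact 95% CI | One-sided 95% upper bound |
|---|---|---|---|
| 0 | 0% | 0 to 16.8% | 13.9% |
| 1 | 5% | 0.1 to 24.9% | 21.6% |
| 2 | 10% | 1.2 to 31.7% | 28.3% |

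One omitted participant changes the proportion by 1/20 = 5 percentage points. The zero-event bound, on which the sample-size statement relies, would be quoted as 13.9% when 21.6% applies. In the any-AE row the change occurs only if that participant had no other unsolicited AE.

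**The case against.** The strongest reply has four parts.

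- *The exceptions cover most cases.* A new episode after the dose may count as increased frequency, and a second infection after full recovery is naturally a new condition. Both points are fair, and they narrow the problem. They do not close it: for a recurring finding such as raised blood pressure, the outcome turns on an undefined judgement.
- *SAP 3.3 is about measured values, while 9.4 is about medical conditions.* This weakens the conflict with 3.3. It does not touch the conflict with the AE definition in SAP 4.5.1.2 and Protocol 8.3.1.
- *Sites follow the protocol, and every reported AE is tabulated.* If the site records the recurrence, the last sentence of the SAP 9.4 paragraph brings it in. The same paragraph, however, says such a condition is not reported as an AE, so the plan gives two answers for one event. Blood pressure would still appear in Table 14.3.5.1, but not in the AE tables.
- *Any error is rare and balanced.* Participants must be healthy at screening, and assessors are blinded, so misclassification should not differ between arms in expectation. This stands, and it is why the point is modest. Balance protects comparisons between arms; it does not protect the absolute rate within an arm.

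**Conclusion.** The point holds as an inconsistency in a stated rule, with a limited effect in one direction. Taken literally, SAP 9.4 leaves out unsolicited conditions that were present at screening, absent at the dose and back afterwards at the same severity, although these are AEs under both documents. The number of such cases is unknown and probably small. Each is worth at most 5 percentage points of an arm's rate, on the assumption that the participant has no other event in that row.

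A reader might go further and infer that the plan counts illness starting between screening and vaccination as treatment-emergent in the primary endpoint. The documents do not support this. Such an illness is not an AE under SAP 4.5.1.2 or Protocol 8.3.1, reporting begins only at vaccination (Protocol 8.2), and no planned table, figure or listing selects on treatment-emergent status. It could enter only if the site recorded it against those rules, or if a missing start day were imputed to the vaccination date under SAP 6.5. Nor is 28 days an amount of misplaced illness; it is the longest possible gap.

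**What to change.** In SAP 9.4:

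1. Define AE baseline as the participant's status immediately before vaccination on Day 1, meaning the screening history updated by the Visit 2 interim history, vital signs and targeted examination. A condition present at that point and unchanged afterwards stays out of the AE tables.
2. Define treatment-emergent as onset, recurrence after resolution, or worsening in severity or frequency after vaccination.

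This brings 9.4 into line with SAP 3.3 and 4.5.1.2 and with Protocol 8.2 and 8.3.1. The cost is a small wording change in one SAP section, with any matching line in the data-entry instructions. Visit 2 already collects what is needed, so no procedure, sample size or table layout changes. It is best made before the unblinded Day 29 safety analysis described in SAP 6.6.

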#### 9.4.1 Primary Summary of Adverse Events

The primary safety objective is to evaluate the safety of adjuvanted and non-adjuvanted formulations of MCV-5 vaccine in healthy adults. To accomplish this objective, an overall summary of adverse events will be presented in Table 14.3.1.1. The table will summarize the number and percentage of participants in each treatment group experiencing the following:

- immediate solicited AEs within 60 minutes post-vaccination;
- solicited local or systemic post vaccination reactogenicity reactions within seven days following vaccination (Days one through seven);
- any SAE;
- any unsolicited AE;
- any Grade 2 or greater solicited local or systemic post vaccination reactions within seven days following vaccination;
- any Grade 2 or greater unsolicited AE;
- any unsolicited AE judged to be related to study product; and
- any Grade 2 or greater unsolicited AE following vaccination judged to be related to study product.

Note: summaries of unsolicited AEs will include SAEs.

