#### 2.4.4. Primary Endpoints

- The occurrence and severity of solicited local and systemic post immunization reactions within seven days following vaccination.
- The occurrence, severity, and relatedness of unsolicited adverse events for 28 days following vaccination, and serious adverse events for 6 months following vaccination.

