## 5.2.6. Visit 4 (Day 29 +14 days)

On Day 29 (plus 14 calendar days if necessary for participant compliance), the participant will return to study site and the following procedures occur:

- a) Obtain interim medical history, including medication use.
- b) Vital signs will be measured.
- c) AEs will be evaluated.
- d) A targeted physical exam will be performed, if indicated.
- e) Urine pregnancy test will be performed.
- f) Blood samples (30 mL) will be obtained for immunological assays (see Appendix I).
- g) The participant will be reminded to contact the study site with any new information about chronic illnesses, serious health events, and/or hospitalizations, and the Day 85 follow-up contact information will be provided. Every effort should be made to adhere to the protocol windows.

Page **44** of **106** 

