#### **Endpoints:**

Summaries by product received including the number and percentage of participants experiencing:

- immediate AEs within 60 minutes post-vaccination;
- solicited local or systemic post vaccination reactogenicity reactions within seven days following vaccination (Days one through seven);
- any SAE within six months following vaccination;
- any AE within 28 days following vaccination;
- any Grade 2 or greater solicited local or systemic post vaccination reactions within seven days following vaccination;
- any Grade 2 or greater unsolicited AE within 28 days following vaccination;
- any unsolicited AE within 28 days following vaccination judged to be related to study product; and
- any Grade 2 or greater unsolicited AE within 28 days following vaccination judged to be related to study product.

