## 8.1. Safety Events

All safety events observed under this protocol are reported through the AdvantageEDC data system throughout the study. Safety events related to vaccine reactogenicity are collected on study-specific forms. Reactogenicity will be collected through the visit on Day 7, if a solicited sign or symptom has started during the seven days post-vaccination and continues it will continue to be reported as a reactogenicity symptom. Only when the reactogenicity event is considered an SAE, as defined below, will it be reported on an AE/SAE form set, in addition to the reactogenicity form. Any symptom starting after seven days post-vaccination will be recorded as an AE. All other

safety events that meet the definition of an AE or SAE that occur throughout the study are reported on the AE/ SAE form set. AE's will be collected through study visit Day 28. SAEs will be assessed through Day 180 and will be reported on the AE/ SAE form set.

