### 14.3 Adverse Events

### **14.3.1 AE** Tables

TABLE 14.3.1.1: Summary of Overall Adverse Events - Safety Population

	MC	vanted CV-5 =X)	MC	uvanted EV-5 =X)	Mena (N=	ectra® =X)
	n	%	n	%	n	%
Solicited Adverse Events						
Any Solicited Adverse Event within 60 minutes post-vaccination	XX	XX.X	XX	XX.X	XX	XX.X
Any Solicited Adverse Event 1-7 days post- vaccination 	XX	XX.X	XX	xx.x	XX	XX.X
Any Local Solicited Event 1-7 days post-vaccination 	XX	XX.X	XX	xx.x	XX	XX.X
Any Systemic Solicited Event 1-7 days post-vaccination 	XX	XX.X	XX	xx.x	XX	XX.X
Any Grade 2 or greater Solicited Local or Systemic Event 1-7 days post-vaccination 	XX	XX.X	XX	XX.X	XX	XX.X
Unsolicited Adverse Events						
Any Serious Adverse Event 	XX	XX.X	XX	XX.X	XX	XX.X
At Least 1 Unsolicited Adverse Event 	XX	XX.X	XX	xx.x	XX	XX.X
Any Grade 2 or greater Unsolicited Adverse Event 	XX	XX.X	XX	xx.x	XX	XX.X
Any Related Unsolicited Adverse Event 	XX	XX.X	XX	xx.x	XX	XX.X
Any Grade 2 or greater Related Unsolicited Adverse Event 	XX	XX.X	XX	XX.X	XX	XX.X

N = Number of participants in the Full Analysis population; n = Number of participants reporting at least one of the specified conditions.

Unsolicited adverse events (AEs) include both serious and non-serious AEs.

A participant is only counted once per row.

<sup>1 Excludes events within 60 minutes of vaccination

<sup>2 Serious adverse events (SAEs) were to be collected for 6 months following vaccination.

<sup>3 Unsolicited AEs were to be reported for 28 days following vaccination.

TABLE 14.3.1.2: Number and Percentage of Participants Experiencing Solicited Events, by Symptom and Treatment Group - Full Analysis Population

		ed MCV-5 =X)		anted MCV-5		actra® =X)	MCV-5 + Adj versus	MCV-5 versus
Symptom	n (%)	(95% CI)	n (%)	(95% CI)	n (%)	(95% CI)	Menactra p-value 	Menactra p-value 
Local Reactions								
Pain at injection site								
Erythema at injection site								
Swelling at injection site								
Any Local Symptom								
Systemic Symptoms								
Fever								
Headache								
Fatigue/malaise								
Joint pain/arthralgia								
Muscle pain/myalgia								
Diarrhea								
Anorexia								
Chills								
Vomiting								
Any Systemic Symptom								
Any Systemic or Local Symptom								

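### SAP 9.4.1 omits the 28-day limit from the four unsolicited-AE rows and folds in SAEs with no onset cut-off, so later events can enter rows labelled 28-day

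*SAP*

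**What the plan says.** **Protocol.** The primary endpoint in 2.4.4 is "The occurrence, severity, and relatedness of unsolicited adverse events for 28 days following vaccination, and serious adverse events for 6 months following vaccination". Section 7.3.1 carries the 28-day limit into each of the four AE rows to be tabulated: any AE, Grade 2 or greater unsolicited ("any Grade 2 or greater unsolicited AE within 28 days following vaccination"), related unsolicited, and Grade 2 or greater related unsolicited ("any Grade 2 or greater unsolicited AE within 28 days following vaccination judged to be related to study product"). SAEs to six months are a separate row. Section 8.1 states that "AE's will be collected through study visit Day 28". The visit that evaluates AEs is Visit 4 in 5.2.6: "On Day 29 (plus 14 calendar days if necessary for participant compliance".

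**SAP.** Section 9.4.1 repeats the four rows with no time limit, although the solicited rows in the same list keep their seven-day limit. It adds "Note: summaries of unsolicited AEs will include SAEs". Section 9.4 states: "All adverse events reported will be included in the summaries and analyses". Sections 4.5.1 and 4.5.1.3 have SAEs collected to Day 180. The 28-day window does appear in the SAP's primary endpoint (3.2.1), in its collection rule (4.5.1) and in footnote 3 on all four unsolicited rows of Table 14.3.1.1: "Unsolicited AEs were to be reported for 28 days following vaccination". The same table states that the unsolicited rows contain serious and non-serious events, and footnote 2 gives SAEs a six-month collection period.

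**The concern.** Three SAP statements act together on the primary safety table: rows with no window, SAEs folded into those rows, and inclusion of everything reported. Nothing in the SAP filters on onset day. The only time split for unsolicited events (9.4.3, Tables 14.3.1.9 and 14.3.1.10) is Days 1-8 against an open-ended later period.

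A programmer who follows 9.4 and 9.4.1 to the letter counts an SAE on Day 150 in the row for at least one unsolicited AE. A programmer who follows 3.2.1 does not. Both can claim to have followed the SAP, yet they can produce different primary results.

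Under the literal reading, the same row could also grow between the interim analysis (safety data to Visit 4, SAP 6.6) and the final analysis, while its footnote still says 28 days.

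**Working it through.** **1. The plan's own figures (protocol 7.4, SAP 5; 20 per arm).**
- Chance of seeing at least one AE with an 11% rate: 1 − 0.89^20 = 0.903. The plan says above 90%.
- One-sided 95% upper bound for 0 of 20: 1 − 0.05^(1/20) = 0.139. The plan says about 14%.

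Both reproduce. Neither depends on the AE window, so the design statement is not affected.

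**2. The passages side by side.**

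| Place | Window for unsolicited AEs |
|---|---|
| Protocol 2.4.4, 7.3.1 | 28 days |
| SAP 3.2.1, 4.5.1 | 28 days |
| SAP Table 14.3.1.1, footnote 3 | 28 days, worded as a reporting period |
| SAP 9.4.1 rows | none stated; SAEs included |
| SAP 9.4 | none; all reported AEs included |
| Protocol 8.1 | ends at a visit, not at an onset day |

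No passage says whether an SAE after 28 days counts in the unsolicited rows. No passage says that AEs with onset on Days 30 to 43 are to be counted, and none removes them if they are recorded.

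**3. Day arithmetic.** Vaccination is Day 1 (SAP 3.3), so Day 29 is 28 days after vaccination. The end of the Visit 4 window is 29 + 14 = Day 43, which is 42 days after. SAE collection to 180 days runs 180 − 28 = 152 days past the AE window.

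**4. Late SAEs.** Assume a six-month SAE rate s and a constant hazard. The late share per participant is 1 − (1 − s)^(152/180). Protocol 13.2 gives 1.0% for Menactra without a stated period, so 1% is used only as an assumption, with a range around it.

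| s | Late share | Expected per arm of 20 | Chance of at least one in 60 |
|---|---|---|---|
| 0.5% | 0.0042 | 0.08 | 22% |
| 1% | 0.0085 | 0.17 | 40% |
| 2% | 0.0169 | 0.34 | 64% |

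These are upper figures for the effect on the rows. A participant already counted for an AE inside the window adds nothing, and the Grade 2 and related rows also need the event to meet those conditions.

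**5. Late Visit 4.** Assume a constant hazard and that events are recorded up to the visit. The tabulated rate is 1 − (1 − p)^(d/28), where p is the 28-day rate and d is days from vaccination to the visit.

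| p | All seen at d = 35 | All seen at d = 42 |
|---|---|---|
| 5% | 6.2% | 7.4% |
| 11% | 13.6% | 16.0% |
| 20% | 24.3% | 28.4% |
| 30% | 36.0% | 41.4% |

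The last column is a ceiling: it needs every participant to attend on Day 43. A participant seen on Day 29 adds no time. The documents give no late-visit rate, so the real effect cannot be computed.

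**6. Unit of movement.** One newly counted participant is 1/20 = 5 percentage points in an arm.

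**The case against.** The strongest reply is that the SAP has not given up the 28-day window. It states it in 3.2.1, in 4.5.1 and in the footnote to the very table that 9.4.1 calls for, so the bullets in 9.4.1 can be read as an incomplete restatement. If collection stops at 28 days, the all-reported-events rule in 9.4 is bounded by it for non-serious AEs. Protocol 7.5.2 also takes all safety data after exposure into the primary safety analysis. An SAE is an AE, so counting SAEs with onset inside 28 days in these rows is correct. The trial is descriptive, SAEs have their own row, and the listings show start date and days post dose, so any out-of-window event would be visible.

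Most of this stands, and it rules out three stronger readings that a reader might infer:

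- *That the 28-day endpoint will not be tabulated.* The documents show a conflict whose outcome depends on programming, not an abandoned endpoint.
- *That a participant seen on Day 43 contributes 42 days of AEs.* This is an inference from SAP 9.4 with protocol 8.1 and 5.2.6. A visit date fixes when events are ascertained and does not by itself extend the onset window. The Day 28 visit in protocol 8.1 is most likely Visit 4 counted in days after vaccination, since the same section calls Visit 3 (Day 8) the Day 7 visit.
- *That the arms would differ.* No mechanism is given in a randomised, single-site trial with blinded participants and assessors.

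The reply does not remove the conflict. Footnote 3 describes a reporting period and is not a filter. It sits on rows that by rule contain SAEs, which footnote 2 says run to six months.

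**Conclusion.** The point holds as an internal conflict in the SAP, with moderate severity. The rules in 9.4 and 9.4.1, applied as written, put an SAE with onset after 28 days into rows labelled 28-day. They could do the same for a later-onset non-serious AE recorded at a late Visit 4.

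The SAE part is small under a constant hazard. At 1% over six months, fewer than one extra participant per arm is expected, although a late SAE somewhere among the 60 is quite possible. The late-visit part has a known ceiling but no estimable size. No sample-size figure changes. The case for correcting it is that these are primary safety rates, that one participant is a visible share of an arm of 20, and that two compliant programs should not be able to disagree.

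**What to change.** - **SAP 9.4.1, 9.4.3 and the unsolicited-AE tables:** restrict every unsolicited row, serious and non-serious, to onset no later than 28 days after vaccination (Day 29). State this as a filter on onset day, and reword footnote 3 of Table 14.3.1.1 to match.
- **SAEs to six months:** report them in the existing separate SAE row and in the SAE listing, with the six-month period restored to the 9.4.1 bullet.
- **Non-serious AEs with onset after Day 29, if recorded:** show them in listings only.
- **Protocol 8.1:** align the reference to a Day 28 visit with Visit 4 and the 28-day onset window.

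The cost is a few lines of SAP text, one onset-day condition in the programs and one sentence in the protocol. No new data are needed. The rule should be fixed before the unblinded interim safety analysis.
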